11.0 Study Timelines

11.1 Describe the anticipated duration needed to enroll all study subjects.

Response: It is anticipated that enrollment of all study subjects will be completed in one to one-and-a-half years.

11.2 Describe the duration of an individual subject's participation in the study. Include length of study visits, and overall study follow-up time.

Response:

Patients will complete two visits (Day 1 and Day 90). Neuropsychological testing will take approximately 1-2 hours during a single visit.

11.3 Describe the estimated duration for the investigators to complete this study (i.e. all data is collected and all analyses have been completed).

Response:

Completion of this study, including primary analyses is expected to be in one to two years.

12.0 Setting

12.1 Describe all facilities/sites where you will be conducting research procedures. Include a description of the security and privacy of the facilities (e.g. locked facility, limited access, privacy barriers). Facility, department, and type of room are relevant. Do not abbreviate facility names.

NOTE: Examples of acceptable response may be: "A classroom setting in the Department of Psychology equipped with a computer with relevant survey administration software," "The angiogram suite at Buffalo General Medical Center, a fully accredited tertiary care institution within New York State with badge access," or, "Community Center meeting hall."

Response: Screening and neuropsychological procedures will be conducted in a private testing room in the Buffalo Neuroimaging Analysis Center (BNAC) at the Buffalo General Hospital. Database entry and data analysis will also occur at the academic offices of Buffalo Neuroimaging Analysis Center (BNAC).

12.2 For research conducted outside of UB and its affiliates, describe:

- *Site-specific regulations or customs affecting the research*
- *Local scientific and ethical review structure*

NOTE: This question is referring to UB affiliated research taking place outside UB, i.e. research conducted in the community, school-based research, international research, etc. It is not referring to multi-site research. UB affiliated institutions include Kaleida Health, ECMC, and Roswell Park Cancer Institute.

Response:

N/A: This study is not conducted outside of UB or its affiliates.

13.0 Community-Based Participatory Research

13.1 Describe involvement of the community in the design and conduct of the research.

NOTE: Community-Based Participatory Research (CBPR) is a collaborative approach to research that equitably involves all partners in the research process and recognizes the unique strengths that each brings. CBPR begins with a

research topic of importance to the community, has the aim of combining knowledge with action and achieving social change to improve health outcomes and eliminate health disparities.

Response:

N/A: This study does not utilize CBPR.

13.2 *Describe the composition and involvement of a community advisory board.*

Response:

N/A: This study does not have a community advisory board.

14.0 Resources and Qualifications

14.1 *Describe the qualifications (e.g., education, training, experience, expertise, or certifications) of the Principal Investigator and staff to perform the research. When applicable describe their knowledge of the local study sites, culture, and society. Provide enough information to convince the IRB that you have qualified staff for the proposed research.*

NOTE: If you specify a person by name, a change to that person will require prior approval by the IRB. If you specify a person by role (e.g., coordinator, research assistant, co-investigator, or pharmacist), a change to that person will not usually require prior approval by the IRB, provided that the person meets the qualifications described to fulfill their roles.

Response: [name] is a board-certified neuropsychologist. All members of the research team will receive extensive training to administer study procedures in this research. They will also undergo required CITI and UBIRB GCP training. They will also be closely supervised by [name].

Describe other resources available to conduct the research.

14.2 *Describe the time and effort that the Principal Investigator and research staff will devote to conducting and completing the research.*

NOTE: Examples include the percentage of Full Time Equivalents (FTE), hours per week. The question will elicit whether there are appropriate resources to conduct the research.

Response: The PI will be adequately accessible to oversee this project. In addition, members of the research team will be dedicated to conducting the project.

14.3 Describe the availability of medical or psychological resources that subjects might need as a result of anticipated consequences of the human research, if applicable.

NOTE: One example includes: on-call availability of a counselor or psychologist for a study that screens subjects for depression.

Response: While there are no anticipated consequences, the PI will be adequately accessible to address any needs. Any unanticipated medical emergencies or incidental findings will be brought to the attention of a neurologist responsible for the care of the patient.

14.4 Describe your process to ensure that all persons assisting with the research are adequately informed about the protocol, the research procedures, and their duties and functions.

Response:

As described above, all research staff will undergo extensive training in administration of neuropsychological tests and they will be closely supervised by neuropsychologist, [name]. They will also be required to undergo all necessary research training protocols before engaging in research activities with participants.

15.0 Other Approvals

15.1 Describe any approvals that will be obtained prior to commencing the research (e.g., school, external site, funding agency, laboratory, radiation safety, or biosafety).

Response:

N/A: This study does not require any other approvals.

16.0 Provisions to Protect the Privacy Interests of Subjects

16.1 Describe how you will protect subjects' privacy interests during the course of this research.

NOTE: Privacy refers to an individual's right to control access to him or herself. Privacy applies to the person. Confidentiality refers to how data collected about individuals for the research will be protected by the researcher from release. Confidentiality applies to the data.

Examples of appropriate responses include: "participant only meets with a study coordinator in a classroom setting where no one can overhear", or "the participant is reminded that they are free to refuse to answer any questions that they do not feel comfortable answering."

Response:

Study procedures are performed in private, noise- and temperature-controlled rooms and will be conducted in the presence of only one designated, trained member of the research team. Study documents are maintained in a locked staff office that is only accessed by designated personnel. Participants are reminded that they are free to refuse to answer any questions at any time. When they contact the research team via telephone they are able to determine the privacy of the settings in which they participate.

16.2 *Indicate how the research team is permitted to access any sources of information about the subjects.*

*NOTE: Examples of appropriate responses include: school permission for review of records, consent of the subject, HIPAA waiver. This question **does apply** to records reviews.*

Response:

After the consent process, the participant controls the research team's access to such information because it was directly provided by the participant through an interview/survey procedure.

17.0 Data Management and Analysis

17.1 *Describe the data analysis plan, including any statistical procedures. This section applies to both quantitative and qualitative analysis.*

Response:

Statistical analyses will be performed using SPSS 22.0 (IBM Inc., Armonk, NY, USA) and R 3.4.1 (The R Foundation).

[1a] Determine whether low Conscientiousness predicts lesser overall cognitive improvement following cognitive rehabilitation in people with MS. The question of whether Conscientiousness predicts successful intervention will be addressed using baseline measures of trait Conscientiousness and cognitive performance before and after rehabilitation. We will assess linear relationships between baseline trait Conscientiousness and overall magnitude of cognitive improvement using linear regression models. Cognitive improvement will be measured according to differences in cognitive scores between baseline assessment during visit 1 and post-rehabilitation assessment at visit 2. In order to summarize results across all cognitive measures, test scores will be converted to normalized z-scores and averaged together.

1b] Determine whether the impact of Conscientiousness on cognitive rehabilitation is moderated by executive function and treatment adherence. In order to address the question of whether or not adherence and executive function moderate the impact of Conscientiousness on intervention success, we intend to add interaction parameters to the linear regression analysis described for aim 1a.

For instance, we will calculate the interaction variable between Conscientiousness and DKEFS-ST (executive function) and include it in our regression models.

[2] Identify structural and functional brain connectome characteristics which predict successful improvement in sub-domains of cognition following rehabilitation. In order to identify brain connectome characteristics which, predict specific responses to sub-domains of cognition following rehabilitation, we intend to employ linear machine/statistical learning techniques, such as partial least squares regression. The correct statistical learning models will be identified at the time of analysis in order to produce the most appropriate predictions. Models will be selected according to the distribution and dimensionality of our connectome variables. Following training of the predictive models, fit of the models will be assessed using k-fold cross validation.

17.2 If applicable, provide a power analysis.

NOTE: This may not apply to certain types of studies, including chart/records reviews, survey studies, or observational studies. This question is asked to elicit whether the investigator has an adequate sample size to achieve the study objectives and justify a conclusion.

Response: Given a 0.38 effect size observed in a previous study of HCs which indicated a relationship between Conscientiousness and successful cognitive training²⁰, power analysis indicated 41 participants would be sufficient for an 80% chance of avoiding type II error.

17.3 Describe any procedures that will be used for quality control of collected data.

Response:

All MRI data has already been reviewed for quality by expert investigators responsible for the CEG-MS study.

Scoring and data entry will be completed and checked by trained staff members under the supervision of the PI.

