1.0 Objectives

1.1 *Describe the purpose, specific aims, or objectives of this research.*

Response: The specific aims of this study are:

[1a] Determine whether low Conscientiousness predicts lesser overall cognitive improvement following cognitive rehabilitation in people with MS.

[1b] Determine whether the impact of Conscientiousness on cognitive rehabilitation is moderated by executive function and treatment adherence.

[2] Identify structural and functional brain connectome characteristics which predict successful improvement in sub-domains of cognition following rehabilitation.

This study will also serve to supplement the sample of participants for the current IRB approved study ((IRB: 603069, Title: *A case-control, 5-year follow-up study of cardiovascular, environmental and genetic risk factors for disease progression in patients with multiple sclerosis (CEG-MS study)*).

1.2 *State the hypotheses to be tested, if applicable.*

NOTE: A hypothesis is a specific, testable prediction about what you expect to happen in your study that corresponds with your above listed objectives.

Response:

[1a] We expect that individuals with low baseline Conscientiousness will experience a lower magnitude of overall cognitive improvement following rehabilitation

[1b] We expect the impact of Conscientiousness on fidelity of rehabilitation will in part be moderated by individual differences in program adherence and executive function

[2a] We expect that individual differences in structural and functional connectome disturbances will in part explain differences in participant responses to cognitive rehabilitation.

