2.0 Scientific Endpoints

2.1 Describe the scientific endpoint(s), the main result or occurrence under study.

*NOTE: Scientific endpoints are outcomes defined before the study begins to determine whether the objectives of the study have been met and to draw conclusions from the data. Include primary and secondary endpoints. Some example endpoints are: reduction of symptoms, improvement in quality of life, or survival. Your response should **not** be a date.*

Response: Our primary end-point are predictive. Our first primary end-point will have been met if baseline measures of personality, as measured by the NEO-Five Factor Inventory (NEO-FFI), will predict overall cognitive improvement following rehabilitation. Likewise, our second primary end-point will have been met if baseline measures of brain connectivity predict specific improvements in cognitive sub-domains, following rehabilitation. Cognitive improvement will be measured according to changes from visit 1 to visit 2 for the following neuropsychological tests: Symbol Digit Modalities Test (SDMT), California Verbal Learning Test 2nd Edition (CVLT), Brief Visuospatial Learning Test Revised (BVMT-R), MS Neuropsychological Screening Questionnaire (MSNQ), Delis-Kaplan Executive Function System (DKEFS) Sorting Test, Tower of London (TOL), Elithorn's Perceptual Maze Test (EPMT).

	Day 0 (Visit 1)	Day 90 (Visit 2)
NEO Five Factor Inventory (NEO-FFI)	X	X
Symbol Digit Modalities Test (SDMT)	X	X
California Verbal Learning Test Second Edition (CVLT)	X	X
Brief Visuospatial Memory Test Revised (BVMT)	X	X
MS Neuropsychological Screening Questionnaire (MSNQ)	X	X
Delis Kaplan Executive Function System Tower Test (DKEFS-TT)	X	X
Delis Kaplan Executive Function System Sorting Test (DKEFS-ST)	X	X
Elithorn's Perceptual Maze Test (EPMT)	X	X
Multiple Sclerosis Quality of Life (MSQoL)	X	X
Beck Depression Inventory Fast Screen (BDI-FS)	X	X
Fatigue Severity Scale (FSS)	X	X

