If an individual is ineligible for participation, their screening information will be discarded (i.e., shredded). If participants are deemed eligible (either in person or over the phone), they will be scheduled to come in to the hospital for neuropsychological testing. Written consent will be obtained prior to administration of tests. As part of the consent process, participants will be asked for permission to use any data collected as part of the screening process as well.

10.2 Describe what data will be collected.

NOTE: For studies with multiple data collection points or long-term follow up, consider the addition of a schedule or table in your response.

Response: Demographic/social history, health history (as provided by participants during screening, review of medical records, etc.), and cognitive test data.

10.3 List any instruments or measurement tools used to collect data (e.g. questionnaire, interview guide, validated instrument, data collection form).

Include copies of these documents with your submission.

Response: Below is a list of neuropsychological tests that will be included. Symbol Digit Modalities Test (SDMT), California Verbal Learning Test 2nd Edition (CVLT), Brief Visuospatial Learning Test Revised (BVMT-R), Delis-Kaplan Executive Function System [DKEFS] Sorting Test, Delis-Kaplan

Executive Function System [DKEFS] Tower Test. Self-report/informant-report surveys have been uploaded. Self-report measures include the Beck Depression Inventory-Fast Screen (BDI-FS), Multiple Sclerosis Neuropsychological Questionnaire (MSNQ), Fatigue Severity Scale (FSS), NEO-FFI personality inventory, Multiple Sclerosis Quality of Life (MSQoL) and Elithorn's Perceptual Maze Test (EPMT). Informant-report measures include the NEO-FFI.

10.4 Describe any source records that will be used to collect data about subjects (e.g. school records, electronic medical records).

Response: We will be collecting MRI and EDSS information for subjects from the database of IRB no. 603069 of CEG- MS study.

*10.5 Indicate whether or not **individual** subject results, such as results of investigational diagnostic tests, genetic tests, or incidental findings will be shared with subjects or others (e.g., the subject's primary care physician) and if so, describe how these will be shared.*

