University at Buffalo Institutional Review Board (UBIRB)

Office of Research Compliance | Clinical and Translational Research Center Room 5018
[name]

Title: Impact of Brain Connectome and Personality on Cognitive Rehabilitation
in Multiple Sclerosis

Statistical analyses will be performed using SPSS 22.0 (IBM Inc., Armonk, NY, USA) and R 3.4.1 (The R Foundation).

[1a] Determine whether low Conscientiousness predicts lesser overall cognitive improvement following cognitive rehabilitation in people with MS. The question of whether Conscientiousness predicts successful intervention will be addressed using baseline measures of trait Conscientiousness and cognitive performance before and after rehabilitation. We will assess linear relationships between baseline trait Conscientiousness and overall magnitude of cognitive improvement using linear regression models. Cognitive improvement will be measured according to differences in cognitive scores between baseline assessment during visit 1 and post-rehabilitation assessment at visit 2. In order to summarize results across all cognitive measures, test scores will be converted to normalized z-scores and averaged together.

[1b] Determine whether the impact of Conscientiousness on cognitive rehabilitation is moderated by executive function and treatment adherence. In order to address the question of whether or not adherence and executive function moderate the impact of Conscientiousness on intervention success, we intend to add interaction parameters to the linear regression analysis described for aim 1a. For instance, we will calculate the interaction variable between Conscientiousness and DKEFS-ST (executive function) and include it in our regression models.

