[2] Identify structural and functional brain connectome characteristics which predict successful improvement in sub-domains of cognition following rehabilitation. In order to identify brain connectome characteristics which predict specific responses to sub-domains of cognition following rehabilitation, we intend to employ linear machine/statistical learning techniques, such as partial least squares regression. The correct statistical learning models will be identified at the time of analysis in order to produce the most appropriate predictions. Models will be selected according to the distribution and dimensionality of our connectome variables. Following training of the predictive models, fit of the models will be assessed using k-fold cross validation.

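### Is the 80% power at 41 participants undermined because the first primary end-point names no personality trait and the second has no power figure?

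*Protocol*

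**What the plan says.** Section 2.1 of the protocol sets two primary end-points. The first is met if "baseline measures of personality, as measured by the NEO-Five Factor Inventory (NEO-FFI), will predict overall cognitive improvement following rehabilitation". For connectivity, "our second primary end-point will have been met if baseline measures of brain connectivity predict specific improvements in cognitive sub-domains". Neither statement gives a trait, a direction, an alpha or a threshold.

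The other sections are more specific. Hypothesis 1a in section 1.2 reads "We expect that individuals with low baseline Conscientiousness will experience a lower magnitude of overall cognitive improvement following rehabilitation". The analysis plan in section 17.1 opens with "Determine whether low Conscientiousness predicts lesser overall cognitive improvement following cognitive rehabilitation in people with MS", and the SAP states for the same aim "We will assess linear relationships between baseline trait Conscientiousness and overall magnitude of cognitive improvement using linear regression models".

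Section 17.2 holds the only power statement: effect size 0.38, taken from a study of healthy controls that related Conscientiousness to training success, and "power analysis indicated 41 participants would be sufficient for an 80% chance of avoiding type II error". It gives no metric, alpha, sidedness or test, and the SAP has no power section. Section 5.1 plans 50 participants.

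On instruments, section 10.3 lists the NEO-FFI among the self-report measures and adds "Informant-report measures include the NEO-FFI". For aim 2, the SAP leaves the choice of learning model to the time of analysis and says "fit of the models will be assessed using k-fold cross validation".

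**The concern.** Section 2.1 is where success is defined, and its wording is wider than the quantity that was powered. The NEO-FFI yields five traits. Read literally, an association with any of them, or with Conscientiousness in the unexpected direction, could be reported as meeting the first primary end-point even though hypothesis 1a had failed. Collecting both self-report and informant forms adds a further choice of predictor.

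If the wide reading governed, one of two things would suffer. Five unadjusted tests would inflate the chance of a false success, while an adjustment could pull power well below 80%. The second primary end-point looks weaker still, since it has no effect size, no power, no share of alpha and no stated mark for success.

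**Working it through.** **Inputs.** Effect size 0.38, 41 participants and 80% power come from protocol section 17.2; the planned 50 comes from section 5.1. Assumed, because neither document says: 0.38 is a correlation r, and alpha is 5%.

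**Step 1: reproduce the stated 41.** With the Fisher transformation, N = ((z_alpha + z_power) / atanh(r))² + 3, and atanh(0.38) = 0.4001.

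- One-sided 5%: ((1.645 + 0.842) / 0.4001)² + 3 = 41.6.
- Two-sided 5%: ((1.960 + 0.842) / 0.4001)² + 3 = 52.0.

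Exact bivariate-normal power, obtained by averaging the noncentral t over the distribution of the predictor, gives:

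| Test of one trait, r = 0.38 | N for 80% | Power at 41 | Power at 45 | Power at 50 |
|---|---|---|---|---|
| One-sided 5% | 41 | 80.5% | – | 87.1% |
| Two-sided 5% | 52 | 70.4% | 74.6% | 79.1% |

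The stated 41 is therefore the exact answer for one trait in the hypothesised direction. Other one-predictor readings of 0.38 miss it: Cohen's f gives 57, f² gives 23, R² gives 15, and a one-sample standardised mean gives 45 (one-sided) or 57 (two-sided). Enrolling 50 allows a loss of (50 − 41) / 50 = 18% before the count falls below 41.

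**Step 2: what the wide reading would cost.** If five independent traits were each tested at 5% without adjustment, the chance of at least one false success would be 1 − 0.95⁵ = 22.6%. With Bonferroni at two-sided 1% per trait, exact power for the one affected trait is 46% at 41 and 57% at 50, and 76 completers are needed for 80%. With one-sided Bonferroni it is 56% and 67%, with about 65 needed.

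**Step 3: is the wide reading planned?** Set side by side:

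| Place | Predictor | Direction |
|---|---|---|
| Protocol 1.1 and 1.2, aim and hypothesis 1a | Conscientiousness | Low trait, less improvement |
| Protocol 17.1, aim 1a | Conscientiousness | Low trait, less improvement |
| SAP, aim 1a | Conscientiousness | Low trait, less improvement |
| Protocol 17.2, power | Conscientiousness | Not stated |
| Protocol 2.1, first primary end-point | Personality measures on the NEO-FFI | Not stated |

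Only section 2.1 is general. No section describes a regression on another trait, so the figures in step 2 have no planned test to attach to.

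**Step 4: does even the wide reading force a loss?** No. Testing Conscientiousness first at one-sided 5%, and other traits only if it succeeds, holds familywise error at 5% and leaves the Conscientiousness test at 80.5% power at 41.

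**Step 5: the second primary end-point.** Power cannot be computed, because the documents give no effect size, alpha or fixed model. If a one-sided 5% were split equally over the two end-points, the Conscientiousness test would run at one-sided 2.5%, which is numerically the two-sided 5% row: 70% at 41 and 79% at 50.

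**The case for a change.** The strongest reply is that intent read from context does not alter a written success rule. Section 2.1 says when the end-point is met, and it says neither Conscientiousness nor a direction. The match at 41 also needs a one-sided test that neither document declares; an analyst who reports a two-sided p-value has 70% power at 41. The choice between self-report and informant form is open, and the second end-point is unsupported however the first is read.

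These observations are accurate, but they do not show that the planned analysis is unsound. The template note in section 2.1 says end-points exist to judge whether the objectives are met, and objective 1a names the trait and the direction. A report claiming success on another trait would have left the written analysis in both documents. On sidedness, the hypothesis is directional, and a two-sided test at the full 50 still gives 79%. On the form, self-report is the natural default: it is completed at the visit, whereas the informant form is taken home and posted back (section 10.1). The connectivity aim is about prediction judged by cross-validation, with the model chosen on the dimensionality of the data. A conventional power figure would need inputs the documents do not have, and a careful reader will treat that result as exploratory.

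**Conclusion.** The concern identifies a loose sentence in section 2.1 and several unstated details, but no error in the sample size and no flaw in the primary analysis. On the correlation reading, 41 is correct for a one-sided 5% test of Conscientiousness, and the planned 50 raises power to 87%. The least favourable reading that stays with the planned single-trait test is two-sided 5%, at 70% with 41 and 79% with 50. The five-trait figures are hypothetical.

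Analysts can fill the gaps from the rest of the plan: Conscientiousness as predictor, the direction in hypothesis 1a, and the self-report form. Section 17.2 cites reference 20, a paper on network measures, for the effect size. Reference 18, the working-memory training study described in section 3.1, appears to be meant. That looks clerical and does not touch the calculation.

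This conclusion assumes that 0.38 is a correlation, that alpha is 5%, and that the regression on Conscientiousness is run as both documents describe. If 0.38 were instead f² for five predictors, 41 would give about 79% to 82%, so that reading would not undermine the figure either, though section 17.2 describes a one-trait relationship.
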